10.6.2. Study Population

10.6.2.1. Subject Disposition

Subject Disposition
Screen Failures

 Screen failures are defined as subjects who consent to participate in the clinical trial but are not

Subject Disposition

subsequently randomized.
 
 ○ At the time of screening closure, there may have been subjects who had been consented but had not been entered into the eCRF. These subjects are not included in the clinical database, but will be noted in a footnote on the Summary of Screening Status and Reasons for Screen Failures. 
 ● Any subject that consented, was entered into the eCRF, and was not randomized, but is missing a screen failure record will have the following values imputed: 
 ○ Was this subject a screen failure? = Yes ○ Reason for screen failure = Missing
Randomized Treatment Discontinuation

 ● Any randomized subject with a non-missing treatment start date that is missing an IP Discontinuation eCRF will have the following values imputed: 
 ○ Date of last dose = See Last Non-Zero Dose Date in Section 10.6.1 ○ Was the study treatment stopped permanently before the scheduled end of the treatment period? = Yes ○ Primary reason the treatment was stopped = Missing
Study Completers/Withdrawals

 ● Any randomized subject that is missing Study Conclusion eCRF will have the following values imputed: 
 ○ Date of subject completion or withdrawal? = See Study Completion/Withdrawal Date in Section 10.6.1 ○ Was the subject withdrawn from the study? = Yes ○ Primary reason for study withdrawal = Missing

Subjects Completion Status
Known Cardiovascular Endpoint Status at End of Study

The following scenarios will be considered as known CV endpoint status at End of Study:
 
 ● Subjects who die during the study ● Subjects who attend a clinic visit within the EOS window ● For the following non-clinic EOS visits, eCRF Visit Contact Details page indicates that a clinical events assessment was able to be performed and date clinical information was assessed is within or after the EOS window: 
 ○ Telephone contact with subject ○ Other contact with subject (mail, email, text, social media, etc.) ○ Designated third party (e.g. family member, caretaker) ○ Health care provider or medical records
Unknown Cardiovascular Endpoint Status at End of Study

The following scenarios will be considered as incomplete CV endpoint status at End of Study:
 
 ● Subjects who withdraw from the study ● EOS visit type = 
 ○ no contact able to be made for this visit ○ survival status search performed but could not confirm that the subject was alive or

Subjects Completion Status

 ○ dead 
 ○ Publicly available sources (e.g., public registry, newspaper) ○ Other, specify ● For the following non-clinic EOS visits, eCRF Visit Contact Details page indicates that a clinical events assessment was not able to be performed or date clinical information was assessed is before the EOS window: 
 ○ Telephone contact with subject ○ Other contact with subject (mail, email, text, social media, etc.) ○ Designated third party (e.g. family member, caretaker) ○ Health care provider or medical records ● eCRF Visit Contact Details page is missing information to determine if a clinical events assessment was performed or the date it was performed.
Known Vital Status at End of Study

The following scenarios will be considered as known vital status at End of Study:
 
 ● Subjects who die during the study, or have a death date ● Subjects who attend a clinic visit within the EOS window ● For the following non-clinic EOS visits, latest date subject last known to be alive is within or after the EOS window. 
 ○ Telephone visit ○ Other contact with subject (mail, email, text, social media, etc.) ○ Designated third party (e.g. family member, caretaker) ○ Health care provider or medical records ○ Publicly available sources (e.g., public registry, newspaper) ○ Other, specify ● For subjects who withdraw from the study, the latest date subject last known to be alive is within or after the EOS window.
Unknown Vital Status at End of Study

The following scenarios will be considered as unknown vital status at End of Study:
 
 ● For subjects who withdraw from the study, the latest date subject last known to be alive is missing or before the EOS window; ● EOS visit type = no contact able to be made for this visit (LTFU subjects only); ● EOS visit type = survival status search performed but could not confirm that the subject was alive or dead (LTFU subjects only); ● For the following non-clinic EOS visits, latest date subject last known to be alive is missing or before the EOS window. 
 ○ Telephone visit ○ Other contact with subject (mail, email, text, social media, etc.) ○ Designated third party (e.g. family member, caretaker) ○ Health care provider or medical records ○ Publicly available sources (e.g., public registry, newspaper) ○ Other, specify

10.6.2.2. Demographic & Baseline Characteristics

Demographic & Baseline Characteristics
Age

 • GSK standard IDSL algorithms will be used for calculating age where birth date will be imputed as follows: 
 ○ Any subject with a missing day will have this imputed as day '15'. ○ Any subject with a missing date and month will have this imputed as '30th June'. • Birth date will be presented in listings as 'YYYY'.
High Level Race

 • Geographic ancestry data will be combined into the following high level race categories: 
 ○ American Indian or Alaskan Native ○ Asian (Asian-East Asian Heritage, Asian-Japanese Heritage, Asian-Central/South Asian Heritage, Asian-South East Asian Heritage, Mixed Asian Race) ○ Black or African American ○ Native Hawaiian or Other Pacific Islander ○ White (White-Arabic/North African Heritage, White-White/Caucasian/European Heritage, Mixed White Race) ○ Mixed Race (Multiple high level races are selected) 
Note: A subject will only be counted in one category. Mixed Asian Race includes subjects who have more than one Asian category selected, but no other categories. Mixed White Race includes subjects who have more than one White category selected, but no other categories.

Race Detail

 • Geographic ancestry data will be combined into race detail categories: 
 ○ American Indian or Alaskan Native ○ Asian-Central/South Asian Heritage ○ Asian-East Asian Heritage ○ Asian-Japanese Heritage ○ Asian-South East Asian Heritage ○ Mixed Asian Race (Only display if data exists) ○ Black or African American ○ Native Hawaiian or Other Pacific Islander ○ White-Arabic/North African Heritage ○ White-White/Caucasian/European Heritage ○ Mixed White Race (Only display if data exists) ○ Mixed Race (Multiple high level races are selected; only display if data exists) 
Note: A subject will only be counted in one category. Mixed Asian Race includes subjects who have more than one Asian category selected, but no other categories. Mixed White Race includes subjects who have more than one White category selected, but no other categories.

Current ESA Use at Randomization

 • Current ESA users at randomization are subjects with a prior ESA type at randomization.
Prior ESA Type and Standardized Prior ESA Dose (U/week) at Randomization

 • During the screening period, subjects may be receiving ESAs in multiple ways, including: epoetin IV or SC, darbepoetin IV or SC, or methoxy PEG-epoetin beta IV or SC.

Demographic & Baseline Characteristics

- A subject’s prior ESA type will be determined from the records that contribute to the subject’s standardized prior ESA dose. The following categories of prior ESA type will be summarized:
 - Darbepoetin alfa only
 - Epoetin only
 - This group contains subjects using any of the following types of epoetin: epoetin alfa, epoetin beta, epoetin lambda, epoetin theta, and epoetin zeta.
 - Methoxy PEG-epoetin beta only
 - This group contains subjects using methoxy PEG-epoetin beta and pegzerepoetin alfa.
 - Multiple
 - This group contains subjects using any combination of the ESA types.
 - Missing

- The dose of ESA will be standardized to obtain a continuous single unit prior ESA dose in terms of epoetin IV U/week for the period from the Week -8 visit to the day before the Randomization date.

- All prior ESA therapy concomitant medication records from screening/run-in will be selected and ordered by start date and end date.

- The standardization will be carried with the following formula:
- For subjects taking epoetin IV:
 - Standardized ESA dose (U/week) = epoetin IV dose (U)*frequency
- For subjects taking epoetin SC:
 - Standardized ESA dose (U/week) = (161/113)*epoetin SC dose(units)*frequency
- For subjects taking darbepoetin IV or SC:
 - Standardized ESA dose (U/week) = 250*darbepoetin dose (µg)*frequency
- For subjects taking methoxy PEG-epoetin beta:
 - Standardized ESA dose (U/week) = 208*methoxy PEG-epoetin beta dose (µg)*frequency

Note: Frequency and Gap Factors defined as follows:

Frequency (from eCRF)	Frequency (for standardization formula)	Gap Factor
One time dose	see below	n/a
Four times per week	4	0.75 day
Three times per week	3	1.33 days
Two times per week	2	2.5 days
Every week	1	6 days
Every 10 days	0.70	9 days
Every 2 weeks	0.50	13 days

Demographic & Baseline Characteristics			
Every 3 weeks	0.33	20 days	
Every 4 weeks	0.25	27 days	
Every 5 weeks	0.20	34 days	
Every 6 weeks	0.167	41 days	
Every 8 weeks	0.125	55 days	

- If the frequency of the record is not 'one time dose', then duration is calculated as follows:
 - If the concomitant medication record start date \geq Randomization date, the duration of the record is 0.
 - If the concomitant medication record end date + gap factor < Week -8 visit date, the duration of the record is 0.
 - If the concomitant medication record end date + gap factor \geq Week -8 visit date, the duration of a record will be calculated as Stop Date – Start Date +1 day, where:
 - Start date will be the latest of (concomitant medication record start date and the Week -8 visit date).
 - Stop date will be the concomitant medication record end date + gap factor.
- If the frequency of the record is 'one time dose', then:
 - If the concomitant medication record start date \geq Randomization date, the duration of the record is 0.
 - If Week -8 visit date \leq concomitant medication record start date, then:
 - Frequency (for standardization formula) = 1
 - Duration = 7 days
 - If concomitant medication record start date < Week -8 visit date, then:
 - Frequency (for standardization formula): $7 / [\text{earliest of (the day before the next sequential prior ESA concomitant medication record start date and the day before randomization)} - \text{start date of record} + 1 \text{ day}]$
 - If the earliest non-missing date of (the day before the next sequential prior ESA concomitant medication record start date and the day before randomization) < Week -8 visit date, the duration of the record is 0.
 - If the earliest non-missing date of (the day before the next sequential prior ESA concomitant medication record start date and the day before randomization) \geq Week -8 visit date, the duration of the record is calculated as Stop Date – Start Date + 1, where:
 - Start date will be the Week -8 visit date.
 - Stop date will be the earliest of (the day before the next sequential prior ESA concomitant medication record start date and the day before randomization)
- The total dose for each prior ESA record will be: Standardized dose*duration/7days
- A weighted mean will then be used to obtain the prior ESA dose:
 Mean prior ESA dose = $[(\text{ESA total dose}_{\text{Record 1}}) + \dots + (\text{ESA total dose}_{\text{Record n}})] / [(\text{Randomization Date} - \text{Week -8 Visit Date}) / 7 \text{ days}]$

Demographic & Baseline Characteristics
Baseline Body Mass Index (BMI)

 Calculated as baseline weight (kg) / [height (m)]²
Dosing Algorithm at Randomization

 Protocol Amendment 3 updated the dosing algorithm used to assign doses of randomized treatment to subjects in both treatment arms. The number of subjects randomized under the original algorithm and under the updated algorithm will be summarized. A subject's randomization date will be compared to the site-specific ethics committee/regulatory protocol amendment approval date for their site. This date is stored in the IRT system as the Site Level Amendment Flag Date for each site. Subjects randomized before their site's non-missing Site Level Amendment Flag Date or who have a missing Site Level Amendment Flag Date will be considered to have been randomized under the original algorithm, and subjects randomized on or after their site's non-missing Site Level Amendment Flag Date will be considered to have been randomized under the updated algorithm.
History of Diabetes

 Subjects are considered to have a history of diabetes if they have a yes response to at least one record of the medical history terms that contains "diabetic" or "diabetes" except anything containing non-diabetic or variations relating to it (e.g. nondiabetic and other spellings) and also 
 DIABETES INSIPIDUS, NEPHROGENIC DIABETES INSIPIDUS If subjects have indicated that they do not have any of the listed diabetic medical history conditions above, they are considered not to have a history of diabetes. If subjects have not been classified as either having or not having a history of diabetes, and are missing a response to any of the listed medical history conditions, their diabetes history status will be missing.
History of Stroke

 Subjects are considered to have a history of stroke if they have a yes response to the stroke medical history condition. Subjects who have indicated that they do not have a history of stroke will be summarized accordingly. If a subject is missing a response to the stroke medical history condition, their stroke history status will be missing.
History of MI

 Subjects are considered to have a history of MI if they have a yes response to either of the following medical history conditions: myocardial infarction, cardiac arrest. Subjects who have indicated that they do not have a medical history of myocardial infarction or cardiac arrest will be considered not to have a history of MI. If subjects have not been classified as either having or not having a history of MI, and are missing a response to either the myocardial infarction or cardiac arrest medical condition, their MI history status will be missing.
History of Cancer

 Subjects are considered to have a history of cancer if they have a yes response to either of the following medical history conditions: neoplasms malignant or unknown/unspecified, allogenic

Demographic & Baseline Characteristics
 
bone marrow transplant.
 
 Subjects who have indicated that they do not have a medical history of neoplasms malignant or unknown/unspecified or allogenic bone marrow transplant will be considered not to have a history of cancer. If subjects have not been classified as either having or not having a history of cancer, and are missing a response to either the neoplasms malignant or unknown/unspecified or allogenic bone marrow transplant medical condition, their cancer history status will be missing.

History of Heart Failure
 
 Subjects are considered to have a history of heart failure if they have a yes response to any of the following medical history conditions: heart failure, left ventricular systolic dysfunction, left ventricular diastolic dysfunction, pulmonary hypertension. Subjects who have indicated that they do not have a medical history of any of the terms listed above will be considered not to have a history of heart failure. If subjects have not been classified as either having or not having a history of heart failure, and are missing a response to any of the medical condition terms listed above, their heart failure history status will be missing.

History of Thromboembolic Events
 
 Subjects are considered to have a history of thromboembolic events if they have a yes response to any of the following medical history conditions: pulmonary embolism, deep vein thrombosis, retinal vein occlusion, arteriovenous graft thrombosis, arteriovenous fistula thrombosis, central venous catheter thrombosis. Subjects who have indicated that they do not have a medical history of any of the terms listed above will be considered not to have a history of thromboembolic events. If subjects have not been classified as either having or not having a history of thromboembolic events, and are missing a response to any of the medical condition terms listed above, their thromboembolic event history status will be missing.

History of Cardiovascular Disease
 
 Subjects are considered to have a history of cardiovascular disease if they have a yes response to any of the following medical history conditions: angina pectoris, myocardial infarction, stroke, coronary artery disease, transient ischaemic attack, heart failure, atrial fibrillation, cardiac arrest, valvular heart disease. Subjects who have indicated that they do not have a medical history of any of the terms listed above will be considered not to have a history of cardiovascular disease. If subjects have not been classified as either having or not having a history of cardiovascular disease and are missing a response to any of the medical condition terms listed above, their cardiovascular disease history status will be missing.

Baseline Iron Use
 
 See Section 10.6.3.

Phosphate Binder Use at Randomization
 
 Phosphate binder use at randomization will be summarized as follows: 
 Iron-based phosphate binders Calcium-based phosphate binders Non-calcium and non-iron based phosphate binders

Demographic & Baseline Characteristics

 ○ No phosphate binder use ● Subjects will be counted in each applicable group, based on the concomitant medications they are receiving on the day of randomization.
Concomitant Medication Use at Randomization

 ● Concomitant medication records on the day of randomization will be used to determine the following classifications of concomitant medication use at randomization: 
 ○ ACEI/ARB ○ Vitamin D ○ Beta blockers ○ SGLT2i ○ Statin ○ Aspirin ○ Vitamin K ○ Insulin ○ Calcimimetics ○ Diabetic medication

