Study Design	
 This is a randomized, open-label (sponsor blind), active-controlled, parallel-group, multi-center, event-driven study in non-dialysis subjects with anemia associated with chronic kidney disease (CKD). This study will comprise 4 study periods: a 4-week screening period, a 4-week placebo run-in period, a treatment period, and a follow-up period. Prior erythropoiesis-stimulating agent (ESA) therapy, if present, continues during the screening and run-in periods. ESAs refer to any rhEPO or methoxy PEG-epoetin beta. The total duration of the study is dependent upon the accumulation of at least 664 adjudicated first MACE (i.e., it is event-driven) unless review of interim data by the Independent Data Monitoring Committee (IDMC) recommends bringing the study to an earlier close. Subjects will be stratified by region, by whether they are currently using an ESA and by participation in the ambulatory blood pressure monitoring (ABPM) sub-study. Region and ESA use at study entry are considered to be stratification factors that are potentially prognostically important, i.e., predictive of study endpoints while participation in the ABPM sub-study is an administrative stratification factor intended solely to ensure a similar number of sub-study subjects in each of the two randomized groups. Following stratification, subjects will be randomized 1:1 to receive oral daprodustat or subcutaneous (SC) darbepoetin alfa.

Overview	Key Elements of the RAP
	
 Both treatment arms (daprodustat and darbepoetin alfa) will follow a protocol-specified randomized treatment dose adjustment algorithm to achieve and/or maintain Hgb within the target range of 10-11 g/dL inclusive. Dose changes will be made programmatically by the Interactive Response Technology (IRT) system for both randomized treatment arms.

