2.3. Study Design

Overview of Study Design and Key Features	

The diagram illustrates the study design timeline. It begins with a 'Screen' phase from Week -8 to Week -4. This is followed by a 'Placebo Run-in' phase where participants continue prior ESA therapy. The main study starts at 'Start of treatment Randomization (Day 1)' with N=4500. The study is divided into a 'Stability period' (Day 1 up to Week 28) and an 'Efficacy Evaluation Period' (Weeks 28-52). A 'Maintenance Period' spans from Week 28 to the end of the study. Two treatment groups are compared: Daprodustat (GSK1278863) and Darbepoetin alfa. The study concludes with a 'Study finish' at 664 adjudicated first MACE events, followed by a 'Follow-up' period of 4-6 weeks after stopping treatment. Key features include: 'Achieve and maintain HemoCue Hgb between 10-11 g/dL', 'Approximately 40% from EU, 30% from RoW, 30% of subjects from US', and 'Not currently on ESA: Hgb 8-10 g/dL, Currently on ESA: Hgb 8-11 g/dL'.
	
Design Features	
 This is a randomized, open-label (sponsor blind), active-controlled, parallel-group, multi-center, event-driven study in ND subjects with anemia associated with CKD.
Dosing and Randomized Treatment Assignment	
 A central randomization approach will be used to protect against potential selection bias due to the open-label design. The randomization schedule will be generated by PPD, and PPD's IRT system will be used for treatment allocation. Subjects will be stratified by region (see Section 10.9.1), by whether they are currently use an ESA and by participation in the ABPM sub-study. Region and ESA use at study entry are stratification factors considered to be potentially prognostically important, i.e., predictive of study endpoints, while participation in the ABPM sub-study is an administrative stratification factor intended solely to ensure a similar number of sub-study subjects in each of the two randomized groups. Following stratification, subjects will be randomized 1:1 to receive oral daprodustat or SC darbepoetin alfa. Please refer to the protocol for starting doses, dose steps and elements of the dose adjustment scheme.

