10.10. Appendix 10: Examination of Covariates, Subgroups & Other Strata

10.10.1. Handling of Covariates, Subgroups & Other Strata

- The following is a non-exhaustive list of covariates that may be used in summaries of demographics, descriptive summaries and statistical analyses.
- Additional covariates of clinical interest may also be considered.
- If the percentage of subjects is small within a particular subgroup, then the subgroup categories may be refined prior to unblinding the trial.
- If the category cannot be refined further, then descriptive rather than statistical comparisons may be performed for the particular subgroup. If there are less than 25 subjects in one of the subgroup categories, any subgroup statistical comparison should be interpreted with caution.
- A pre-specified strategy for prioritizing subgroups/covariates is defined below (as recommended in the 2015 draft Committee for Medicinal Products for Human Use (CHMP) guidance on the investigation of subgroups in confirmatory clinical trials)
- The co-primary and principal secondary endpoints will be evaluated for the subgroups below. Although subgroup analyses are aimed to assess for consistency with the overall results, they may have low power, especially if the subgroup is small or has a low number of events. Statistical models (Cox Proportional Hazards or ANCOVA) will be adjusted for the covariates used in the original analysis, subgroup, treatment and treatment by subgroup interaction. For the prognostic randomization stratification factors (region and current ESA use), the actual status of the factor derived from the eCRF will be used (see Section 10.10.2). For the subgroup Regions combined (USA vs. non-USA), the randomization stratification factor Region (with 5 levels, Regions 1- 5) will not be included in the statistical model. For the subgroup analyses by baseline Hgb group (categorical), the baseline Hgb (continuous) will not be included in the statistical model.

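### The eCRF-derived current-ESA-use status is borrowed from the prior-dose averaging rule, so one isolated ESA dose before Week -8, however old, makes a subject a current user

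*SAP*

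**What the plan says.** Section 10.6.2.2 gives current ESA use no test of its own: "Current ESA users at randomization are subjects with a prior ESA type at randomization". Type in turn comes from the dose calculation. The "prior ESA type will be determined from the records that contribute to the subject", and the sentence goes on to that subject's standardized prior dose. The dose is an average "for the period from the Week -8 visit to the day before the Randomization date".

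Two kinds of record are treated differently:

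- **Recurring records** get zero duration if end date plus gap factor falls before the Week -8 visit. Gap factors run up to 55 days (every 8 weeks).
- **One-time doses before Week -8** have their own branch. Both the frequency and the stop date use the earlier of "the day before the next sequential prior ESA concomitant medication record start date and the day before randomization". The branch sets no maximum age.

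Section 10.10.1 then says, for the subgroup models: "For the prognostic randomization stratification factors (region and current ESA use), the actual status of the factor derived from the eCRF will be used". Section 10.10.2 takes the same source for subgroup summaries. It keeps the IRT stratum for the adjusted analysis models, as do Sections 7.1.2.5 and 7.2.2 for the co-primaries.

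**The concern.** The averaging rule answers how much ESA a subject received per week before randomization. For that purpose, spreading an old single dose thinly does little harm, because the contribution shrinks with age. Reused as a yes/no status, the same rule behaves badly: any non-zero contribution counts in full.

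The design treats current use as a real distinction. Prior ESA "therapy, if present, continues during the screening and run-in periods", and the Section 2.3 design overview gives separate haemoglobin limits: "Not currently on ESA: Hgb 8-10 g/dL, Currently on ESA: Hgb 8-11 g/dL". Section 10.10.1 lists current ESA use among the key subgroups and analyses it for MACE, the principal secondary safety endpoints and haemoglobin. A subject with one remote dose and nothing since would sit in the user group there. That dilutes the comparison between subjects switching from an ESA and those not on one. The same subject would also enter the prior-dose subgroup, normally in the category below 3,000 U/week.

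**Working it through.** The SAP states no figure on this point, so the check applies its duration rules to example records.

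**Inputs.** Randomization is day 0. The Week -8 visit is taken at day -56, an assumption from nominal visit timing. Gap factors and dose conversions are those of Section 10.6.2.2. The doses in the examples are assumed.

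**Rules as formulas** (D = duration in days; D > 0 means the record contributes, so the subject has a type and is a user)

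- Recurring record: D = 0 if end + gap < -56; otherwise D = (end + gap) - max(start, -56) + 1.
- One-time dose on day s < -56: let e = min(next record start - 1, -1). Frequency = 7 / (e - s + 1). D = 0 if e < -56; otherwise D = e + 56 + 1.

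For a one-time dose, s enters the frequency but not D. With no later record, e = -1 and D = -1 + 56 + 1 = 56, the whole window, for every s.

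**One-time darbepoetin dose of 60 µg, no later record** (250 × 60 = 15,000 U before the frequency factor)

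| Day of dose | Frequency | D | Standardized dose (U/week) | Status |
|---|---|---|---|---|
| -120 | 7/120 = 0.0583 | 56 | 875 | user |
| -365 | 7/365 = 0.0192 | 56 | 288 | user |
| -730 | 7/730 = 0.0096 | 56 | 144 | user |
| -1825 | 7/1825 = 0.0038 | 56 | 58 | user |

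**One-time epoetin 10,000 U IV on day -364.** 10,000 × 7/364 = 192 U/week. The total is 192.3 × 56/7 = 1,538 U, and over 8 weeks that is again 192 U/week. The type is epoetin only, the status is user, and the dose group is below 3,000 U/week.

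**Recurring course for contrast.** For an every-2-week course from day -200 to day -100, end + gap = -100 + 13 = -87, which is before -56. D = 0 and the subject is a non-user. Even at the longest gap factor, a recurring course must end no earlier than -56 - 55 = day -111 to count.

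**When the branch decides the status.** If another ESA record starts on or before the Week -8 visit, the old dose drops out. For example, a dose on day -365 followed by a record starting on day -200 gives e = -201 < -56, so D = 0. If a later record starts inside the window, that record contributes by itself (a recurring one has end + gap ≥ start ≥ -56; a one-time dose gets 7 days). The carry-forward therefore settles user status only for a subject with no other contributing ESA record.

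**The case against.** The strongest reply is that such records may hardly exist. Section 10.6.2.2 selects prior ESA records from screening and run-in. How far back the eCRF collected them, and what recent exposure the entry criteria allowed, are matters for the protocol and eCRF guidance, which are not at hand. That stands as a limit on size. It does not remove the defect, because a branch written for one-time doses before Week -8 shows that they are in scope.

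A reader might go further and fault the recurring-record rule as well, since a weekly course ending on day -62, a 4-weekly one on day -83 or an 8-weekly one on day -111 still makes a user. The SAP does not support that. It describes the stratification factor as ESA use at study entry, with therapy continuing through run-in. A course whose own dosing interval reaches Week -8 is a defensible marker of that.

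A reader might also infer that the error only ever adds users, or that the subjects concerned entered under the non-user haemoglobin limits. Neither is shown. An IRT user with no eCRF ESA record would have no prior ESA type, and nothing says which limits a given subject was screened under.

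Finally, subgroup results here are checks of consistency without multiplicity adjustment, and using actual eCRF status for them is a deliberate, stated choice. Both are true. They limit the consequence but do not justify the one-time-dose rule.

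**Conclusion.** The point holds for the one-time-dose branch. As written, a subject whose only contributing ESA record is a one-time dose before Week -8 is a current user regardless of the dose's age, provided it was recorded. This conflicts with the cut-off that the same section applies to recurring records.

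The reach is the current-ESA-use subgroup analyses and summaries, the ESA covariate in the other subgroup models, and the prior-dose subgroup. A reader might infer that the co-primary tests are exposed too. They are not: the ANCOVA and Cox models are specified with the as-randomized stratum. The haemoglobin imputation step uses the label current ESA use at randomization without naming a source. Section 10.10.2 assigns the IRT stratum to adjusted analysis models, so a leak into the primary result is not established.

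No percentage of misplaced subjects can be derived, because the SAP gives neither the number of remote one-time doses nor the share of users. The number may be small or nil. The day counts rest on Week -8 falling at day -56. The absence of an age limit does not depend on that.

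**What to change.** In Section 10.6.2.2, define current ESA use separately from the average dose:

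- A one-time dose before Week -8 does not by itself confer user status. Alternatively, it does so only if its start date plus a stated gap factor reaches the Week -8 visit, as for recurring records. That gap factor should be no longer than the longest one listed (55 days, so no earlier than day -111).
- Leave the recurring-record rule as it is. Requiring end date plus gap factor to reach the day before randomization would be worse: a weekly user last dosed on day -8 gives -8 + 6 = -2 and would become a non-user.
- Tabulate IRT against eCRF ESA status, and repeat the ESA-use subgroup by IRT stratum as a check.

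The cost is one derivation and one table, plus the repeated subgroup display, all from data already collected. A few subjects with an isolated earlier dose would move to the non-user group.
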